5.2.3.1 Treatment Discontinuation Recommendations Related to Liver Safety

In the absence of an explanation for increased liver function tests (LFTs), such as viral hepatitis, preexisting or acute liver disease, or exposure to other agents associated with liver injury, the patient may be discontinued from the study treatment. The investigator may determine that it is not in the patient's best interest to continue study treatment.

Discontinuation of treatment should be considered if:

- ALT or AST $>8 \times$ ULN
- ALT or AST $>5 \times$ ULN for more than 2 weeks
- ALT or AST $>3 \times$ ULN and total bilirubin $>2 \times$ ULN or international normalized ratio (INR) >1.5 (if INR testing is applicable/evaluated)
- ALT or AST $>3 \times$ ULN with the appearance of symptoms suggestive of liver injury (e.g., right upper quadrant pain or tenderness) and/or eosinophilia ($>5\%$)

These treatment discontinuation recommendations are based on the FDA Guidance for Industry (Drug-Induced Liver Injury: Premarketing Clinical Evaluation, July 2009). The recommendations are a basic guide to the investigator based on accumulated clinical experience with drugs in development, and are not specific to clinical experience with enfortumab vedotin.

See [Appendix E](#) for recommended liver safety monitoring and assessment criteria in patients with Grade 2 or greater elevations in ALT, AST, or bilirubin.

5.2.4 Storage and Handling

Refrigeration should be set at 2–8°C for storage of vials and solutions containing enfortumab vedotin. The controlled location must be accessible only to the pharmacist, the investigator, or a duly designated person. Study drug must be reconstituted before administration. Please refer to the Pharmacy Binder for information regarding stability of reconstituted study drug.

The effect of light on the study drug has not been assessed; therefore, it is recommended that vials of enfortumab vedotin lyophilized powder, reconstituted drug product and/or dosing solutions be protected from light until the time of use.

Do not shake reconstituted vials of the study drug.

Any partially used vials or prepared dosing solutions should be destroyed by the site according to institutional drug disposal procedures. Unused vials should be destroyed by the site or returned to the sponsor after authorization by the sponsor or designee. Drug accountability procedures are provided in the Pharmacy Binder.

5.2.5 Packaging and Labeling

Refer to the Pharmacy Binder for information regarding packaging and labeling.

5.2.6 Preparation

Recommended safety measures for handling and preparation include masks, protective clothing, gloves (double glove with nitrile gloves), and vertical laminar airflow safety cabinets.

Detailed drug preparation instructions are provided in the Pharmacy Binder.

5.3 Concomitant Therapy

All concomitant medications and blood products will be recorded from Day 1 (predose) through the safety reporting period (30 days after the last study treatment). Any concomitant medication given for a study protocol-related adverse event should be recorded from the time of informed consent.

5.3.1 Required Concomitant Therapy

There are no required concomitant therapies.

5.3.2 Allowed Concomitant Therapy

Concomitant chronic prednisone (or equivalent) may be used at a dose of ≤ 20 mg/day. Higher doses of prednisone (or equivalent) are permitted for limited duration to treat acute conditions that arise during the study as medically indicated. The use of anti-emetics are permitted. Premedications for IRRs per [Section 5.4.1](#) are permitted.

Therapy to manage enfortumab vedotin-associated toxicity as recommended in [Section 5.2.3](#) are permitted, including growth factors, and transfusions.

Patients who are receiving strong CYP3A4 inhibitors or P-glycoprotein (P-gp) inhibitors concomitantly with enfortumab vedotin should be closely monitored for adverse reactions.

Routine prophylaxis with vaccines is permitted; it is recommended that vaccines used do not contain live micro-organisms.

Palliative radiotherapy on a non-target bone lesion that is not progressing is allowed after 3 cycles of treatment; must be administered after the initial response assessment and repeat scans described in [Section 7.2](#). This will not be considered a subsequent anticancer therapy, but must not interfere with the assessment of tumor target lesions. Treatment with enfortumab vedotin should be interrupted during palliative radiotherapy.

Patients with a positive hepatitis B surface antigen and/or antihepatitis B core antibody and a negative PCR assay at baseline should receive appropriate antiviral prophylaxis or regular surveillance monitoring as per local or institutional guidelines.

5.3.3 Prohibited Concomitant Therapy

Patients may not receive other investigational drugs, radiotherapy (except palliative radiotherapy as described in [Section 5.3.2](#)), or systemic anti-neoplastic therapy during the treatment period. Patients who receive prohibited concomitant therapy must be discontinued from the study.

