3 INVESTIGATIONAL PLAN

3.1 Summary of Study Design

This is a single-arm, open-label, multicenter trial designed to assess the efficacy and safety of enfortumab vedotin as a single agent in locally advanced or metastatic urothelial cancer patients who have previously received systemic therapy with a CPI. Patients must also either have received prior treatment with platinum-containing chemotherapy (Cohort 1) or received

[figure not shown]
no prior platinum-containing or other chemotherapy and are ineligible for treatment with cisplatin at time of enrollment. (Cohort 2). Patients must have progressive disease (PD) during or following their most recent therapy. There are no limits for prior lines of therapy, including taxanes.

Enfortumab vedotin at a dose of 1.25 mg/kg will be administered as an intravenous (IV) infusion over approximately 30 minutes on Days 1, 8, and 15 of each 28-day cycle. Measures of anticancer activity will be assessed by computed tomography (CT scans with contrast, unless contraindicated) every 8 weeks (± 1 week) timed from Cycle 1 Day 1 during treatment. After 1 year on study the frequency of response assessments will be reduced to every 12 weeks (± 1 week). Patients will continue to receive study treatment until disease progression, unacceptable toxicity, investigator decision, consent withdrawal, start of subsequent anticancer therapy, pregnancy, or study termination by the sponsor. After discontinuation of study treatment, patients will be followed every 8 weeks (± 1 week) for response assessments, Eastern Cooperative Oncology Group (ECOG) performance status, and physical exams. After 1 year on study the frequency of follow up visits including response assessments will be reduced to every 12 weeks (± 1 week). Patients that have radiologically-confirmed disease progression (per RECIST 1.1 as determined by the investigator) or have begun subsequent anticancer therapy will be contacted every 8 weeks (± 1 week) up to 1 year on study, and every 12 weeks (± 1 week) thereafter to obtain information on subsequent anticancer therapy, and survival status until death, study closure, withdrawal of consent, or patient is lost to follow-up, whichever occurs first (see [Figure 1](#)). The study will be closed 5 years after enrollment of the last patient, or when no patients remain in long-term follow-up, whichever occurs first. Additionally, the sponsor may terminate the study at any time.

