4.3.1 Discontinuation of Study Treatment

A patient's study treatment may be discontinued for any of the following reasons:

- PD
- AE
- Investigator decision
- Patient decision, non-AE
- Study termination by sponsor
- Other, non-AE
- Pregnancy

Patients who discontinue from study treatment will remain on study for follow-up unless they withdraw consent.

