4.3.2 Patient Withdrawal From Study

Any patient may be discontinued from the study for any of the following reasons:

- Patient withdrawal of consent
- Study termination by sponsor
- Lost to follow-up
- Death
- Other

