6.6 Follow-up (Every 8 Weeks [± 1 week])

Prior to initiation of subsequent anticancer therapy or radiologically-confirmed disease progression (per investigator according to RECIST), patients will have the assessments listed below done 8 weeks (± 1 week) after the previous response assessment scan and every 8 weeks (± 1 week) following the previous visit thereafter until radiologically-confirmed disease progression (per investigator according to RECIST), initiation of a new anticancer therapy, patient death, study closure, or withdrawal of consent, whichever comes first. After 1 year on study the frequency of visits including response assessments will be reduced to every 12 weeks (± 1 week).

- Physical exam
- ECOG performance status
- CT scan with contrast (if contraindicated, see [Appendix F](#)) of the chest, abdomen, pelvis and any other region of known or suspected disease (with repeat scans 4 weeks [$+1$ week] after first documentation of response). Brain and/or bone scans should also be repeated at this timepoint if metastases were identified at baseline, or if metastasis is suspected. Following confirmation scans, response assessments should continue with the previous scan schedule (i.e., the schedule should not be adjusted). Tumor imaging should also be performed whenever disease progression is suspected.

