6.7 Long-term Follow-up (Every 8 Weeks [± 1 week])

After initiation of subsequent anticancer therapy or radiologically-confirmed disease progression (per investigator according to RECIST), patients will be contacted every 8 weeks (± 1 week) after EOT (or 8 weeks from previous protocol visit, whichever is later) for survival status and collection of subsequent anticancer therapy information until death, study closure, or withdrawal of consent, or patient is lost to follow-up, whichever occurs first. After 1 year on study, the frequency of contacts will be reduced to every 12 weeks (± 1 week).

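### Protocol 5.3.3 removes patients given prohibited therapy from the study, while the follow-up sections keep them under survival contact; followed literally it censors OS, by an amount and in a direction the documents do not settle

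*Protocol*

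**What the plan says.** The protocol treats stopping study treatment and leaving the study as separate events. On the first, 4.3.1 says: "Patients who discontinue from study treatment will remain on study for follow-up unless they withdraw consent". On the second, 4.3.2 opens with "Any patient may be discontinued from the study for any of the following reasons" and lists consent withdrawal, sponsor termination, loss to follow-up, death and Other. Prohibited therapy is not named.

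Section 5.3.3 bars other investigational drugs, radiotherapy outside the 5.3.2 exception, and systemic anti-neoplastic therapy during the treatment period. It then says: "Patients who receive prohibited concomitant therapy must be discontinued from the study". That is the study-exit phrase of 4.3.2, not the treatment-stop phrase of 4.3.1.

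Section 3.1 includes among the reasons for ending study treatment "consent withdrawal, start of subsequent anticancer therapy, pregnancy, or study termination by the sponsor". It goes on to say that patients who "have begun subsequent anticancer therapy will be contacted every 8 weeks". Section 6.7 agrees: "After initiation of subsequent anticancer therapy or radiologically-confirmed disease progression (per investigator according to RECIST), patients will be contacted every 8 weeks". Protocol 7.8.2, Appendix A footnote M and SAP Section 4 repeat the rule.

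Section 5.3.2 exempts only the permitted palliative radiotherapy: "This will not be considered a subsequent anticancer therapy, but must not interfere with the assessment of tumor target lesions".

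OS is censored at the last date known alive (Protocol 9.2.5, SAP 7.5.6).

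**The concern.** A patient who receives another systemic anticancer drug while on study treatment falls under two opposite instructions. Section 5.3.3 takes the patient off the study; 3.1 and 6.7 keep the site in contact until death or another listed ending. A site that obeys 5.3.3 stops asking about survival, and that patient's OS is censored when the therapy is given.

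Kaplan-Meier estimation assumes that censoring is unrelated to prognosis. Needing or choosing an unplanned therapy may well be related to it. If these patients do worse than the rest, reported OS is too high; if they do better, it is too low.

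For prohibited therapy that is not anticancer therapy, a literal study exit also stops scans that would otherwise continue under 6.6. That reaches DOR and PFS and, through a lost confirmation scan, possibly ORR.

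**Working it through.** **Step 1. The texts side by side**

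| Prohibited therapy | What 5.3.3 implies if read literally | What the other sections say |
|---|---|---|
| Systemic anticancer therapy | Off study, no survival contact | Contact continues (3.1, 6.7, 7.8.2, footnote M, SAP 4): direct contradiction |
| Investigational drug that is not an anticancer therapy | Off study, no scans or contact | Remains on study (4.3.1), though Other in 4.3.2 could cover an exit |
| Palliative radiotherapy to a stable non-target lesion, outside the bone-only and timing limits of 5.3.2 | Off study, no scans or contact | SAP 7.5.3 does not treat it as new therapy and would keep using the patient's scans |

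**Step 2. Which endpoints are touched**

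- New anticancer therapy: SAP 6.4.2 already drops later responses. Protocol 9.2.2 and SAP 7.5.3 already censor DOR at the last assessment before the new therapy, and Protocol 9.2.4 and SAP 7.5.5 apply the same rule to PFS. ORR, DOR and PFS are therefore essentially unchanged. OS is the endpoint exposed.
- The other two rows: these SAP rules do not apply. Section 6.6 would keep scanning, since "Prior to initiation of subsequent anticancer therapy or radiologically-confirmed disease progression (per investigator according to RECIST), patients will have the assessments listed below". Literal exit would end the scans and censor DOR and PFS early. A responder whose confirmation scan is lost becomes a non-responder (Protocol 9.2.1, SAP 6.5).

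**Step 3. Plan figures**

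The plan gives no figure on this point. Its power figures concern ORR and do not depend on 5.3.3. They reproduce: with 17 or more responders of 100, exact one-sided alpha is 0.0206, and power is 97.9% at an ORR of 25% (stated 98%) and 80.8% at 20% (stated 81%).

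**Step 4. Illustration for OS**

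Inputs:
- Median OS M: 7.4 months (the chemotherapy comparator quoted in Protocol 1.2) or 12 months (assumed).
- Share q of all patients who actually receive prohibited therapy: 2% or 10% (assumed).
- Time of therapy u: uniform over months 1 to 5 (assumed).
- Death hazard afterwards multiplied by h: 0.5 to 2 (assumed).

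Formulas, with λ = ln 2 / M and S0(t) = exp(-λt):
- Chance of being alive at u: A = (exp(-λ) - exp(-5λ)) / (4λ). This is 0.759 for M = 7.4 (λ = 0.0937) and 0.843 for M = 12 (λ = 0.0578).
- Patients who die before u never receive the therapy, so the share set for it at baseline is p = q/A. For q = 2%, p is 2.63% or 2.37%; for q = 10%, 13.2% or 11.9%.
- True survival: S(t) = (1-p)·S0(t) + p·average over u of exp(-λu - hλ(t-u)), for t beyond u.
- Kaplan-Meier with these patients censored at u estimates S0(t). Shift = median of S0 minus median of S.

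| M | q | h = 0.5 | h = 1 | h = 2 |
|---|---|---|---|---|
| 7.4 | 2% | -0.07 | 0 | +0.09 |
| 7.4 | 10% | -0.35 | 0 | +0.44 |
| 12 | 2% | -0.12 | 0 | +0.16 |
| 12 | 10% | -0.65 | 0 | +0.79 |

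Shifts are in months; plus means reported OS is too long. Example: for M = 12, q = 10%, h = 2, the true median is 11.21 and the estimate reads 12.00.

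For scale, the standard error of a median at n = 100 is sqrt(0.25/100)/(0.5λ), which is 1.07 months (M = 7.4) or 1.73 months (M = 12). The 95% half-widths are 2.1 and 3.4 months.

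A wider case shows how far this depends on frequency. With M = 12, p = 20% set for therapy at month 3 and h from 0.5 to 3, the true median runs from 13.14 to 9.97, a shift of -1.14 to +2.03 months.

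**The case against.** The best defence is that 5.3.3 is a deliberate, specific rule. The Amendment 4 rationale says its purpose is that such patients do not carry on in the study, and the sentence is still there in Amendment 9. The consent exception in 4.3.1 cannot be exhaustive, because 4.3.2 allows other exits, including Other. The harm also requires a site to follow one sentence against several that keep contact going.

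Part of this stands. The departure from 4.3.1 taken alone is soft, and a flat contradiction exists only where the therapy is anticancer therapy. That contradiction remains: 7.8.2 and footnote M list what ends survival contact, and prohibited therapy is not on either list. The amendment rationale makes the literal reading more likely at a site.

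A reader might go further and infer that the sponsor meant survival follow-up to stop. No section says so, and those two lists point the other way. A reader might also infer that OS will be overstated. The documents say nothing about the prognosis of these patients, and the sign reverses with it.

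**Conclusion.** The inconsistency is real and minor. For anticancer therapy, 5.3.3 contradicts the follow-up sections; for other prohibited therapy, it departs from a default that 4.3.2 arguably lets it override. OS is a secondary endpoint summarized without a test, and sample size, alpha and power are untouched.

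The size and direction of any OS bias are unknown. The shifts of -0.12 to +0.16 month (2% affected) and -0.65 to +0.79 month (10%) at a 12-month median rest on assumed frequency, timing and hazard, and on sites applying 5.3.3 literally. They lie within sampling error, but calling the effect small would rest on an assumed frequency.

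Two broader readings are not supported. One is that the primary analysis is undermined: only the uncommon routes in Step 2 reach ORR, and nothing shows that they occur. The other is that response endpoints are safe throughout: that holds for new anticancer therapy, not for a non-anticancer drug or for radiotherapy that SAP 7.5.3 does not count as new therapy.

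**What to change.** 1. In Protocol 5.3.3, require that these patients stop study treatment and stay in follow-up: under Section 6.7 if the therapy is an anticancer therapy or the patient has progressed, otherwise under Section 6.6.
2. In Protocol 4.3.2, state that prohibited therapy is not in itself a reason for study withdrawal.
3. Patients sent to 6.6 keep being scanned, so add one clause to SAP 6.4.2 and 7.5.3. It should say whether responses and assessments after a prohibited investigational drug or non-permitted radiotherapy count. The default for analysis should be to treat these as new anticancer therapy, so that the change does not let responses after another drug into the primary endpoint.

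The cost is one sentence and one clause in the protocol, one short SAP clause, and continued follow-up of what is probably a small number of patients at visits and contacts that already exist.

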5.4 Management of Adverse Reactions

5.4.1 Management of Infusion Reactions

An IRR may occur during the infusion of study treatment. The infusion should be administered at a site properly equipped and staffed to manage anaphylaxis should it occur. All supportive measures consistent with optimal patient care should be given throughout the study according to institutional standards. Supportive measures may include administering medications for IRRs.

Patients who have experienced an IRR may be premedicated for subsequent infusions. Premedication may include pain medication (e.g., acetaminophen or equivalent), an antihistamine (e.g., diphenhydramine hydrochloride), and a corticosteroid administered 30–60 minutes prior to each infusion or according to institutional standards. Should a patient experience IRRs in the setting of premedication, continued treatment with enfortumab vedotin must be discussed with the medical monitor prior to the next planned dose.

If anaphylaxis occurs, study treatment administration should be immediately and permanently discontinued.

5.4.2 Management of Hyperglycemia

Investigators should monitor blood glucose levels and are advised to perform additional assessments if any symptoms of hyperglycemia are observed, including a thorough evaluation for infection. In addition, if steroids are used to treat any other condition, blood glucose levels may require additional monitoring. If elevated blood glucose levels are observed, patients should be treated according to local standard of care and referral to endocrinology may be considered.

Patients, especially those with a history of or ongoing diabetes mellitus or hyperglycemia, should be advised to immediately notify their physician if their glucose level becomes difficult to control or if they experience symptoms suggestive of hyperglycemia such as frequent urination, increased thirst, blurred vision, fatigue, and headache.

Patients who enter the study with an elevated HbA1c ($\geq 6.5\%$) at baseline should be referred to an appropriate provider during Cycle 1 for glucose management. Blood glucose should be checked prior to each dosing and dose should be withheld for blood glucose >250 mg/dL (Grade 3 or higher), regardless of relatedness to enfortumab vedotin. Dosing may continue once the patient's blood glucose has improved to ≤ 250 mg/dL (\leq Grade 2) and the patient is clinically and metabolically stable. Patients with blood glucose >500 mg/dL (Grade 4) considered unrelated to enfortumab vedotin may continue dosing once the patient's blood glucose has improved to ≤ 250 mg/dL (\leq Grade 2) and the patient is clinically and metabolically stable. Blood glucose >500 mg/dL (Grade 4) considered related to enfortumab vedotin requires treatment discontinuation. If a patient experiences new onset diabetes mellitus, evaluate patients with a metabolic panel, urine ketones, glycosylated hemoglobin, and C-peptide to assess for new onset type 1 diabetes in the setting of prior CPI.

5.4.3 Management of Rash Related to Enfortumab Vedotin

Enfortumab vedotin is a Nectin-4 directed antibody drug conjugate. Nectin-4 is a cell adhesion molecule that is highly expressed in urothelial carcinoma. Low to moderate levels of Nectin-4 are also expressed on normal tissues, including skin keratinocytes, sweat glands and hair follicles; thus, skin reactions are anticipated events. As such, skin reactions are adverse events of interest in all clinical studies with enfortumab vedotin.

A cumulative review of post-marketing safety data from 18 Dec 2019 (the approval date of enfortumab vedotin in the US) through 22 Oct 2020 identified reports of severe cutaneous adverse reactions in 15 patients receiving enfortumab vedotin, some of whom had fatal outcomes. These reactions occurred predominantly during the first cycle of treatment. Adverse events reported in these cases included SJS (5 cases), blister (3 cases), dermatitis bullous (3 cases), symmetrical drug-related intertriginous and flexural exanthema (SDRIFE; 2 cases), and 1 case each of dermatitis exfoliative, exfoliative rash, epidermal necrosis, oropharyngeal blistering, stomatitis, and TEN.

In enfortumab vedotin monotherapy studies of urothelial carcinoma, serious adverse events of severe cutaneous adverse reactions were reported in 11 of 749 subjects (1.5%) and

included dermatitis bullous (0.4%), drug eruption (0.4%), blister (0.1%), conjunctivitis (0.1%), SJS (0.1%), stomatitis (0.1%), and toxic skin eruption (0.1%).

Subjects should be informed that rash and severe skin reactions have occurred after administration of enfortumab vedotin and advised to contact the Investigator immediately if they have signs and symptoms of skin reactions, oral mucosal and ocular abnormalities including mucositis or conjunctivitis. Starting in the first cycle and throughout treatment, closely monitor subjects for skin reactions. For mild to moderate skin reactions, consider appropriate treatment, such as topical corticosteroids and antihistamines as clinically indicated. For recommendations regarding dose modifications for skin reactions due to enfortumab vedotin, refer to [Section 5.2.3](#).

